## Protocol (last update on January 11, 2019)

A concussion, or mild traumatic brain injury (i.e. mTBI) is a complex pathophysiologic process that is caused by traumatic biomechanical forces to the head [1]. There are an estimated 1.6–3.8 million sport-related concussions every year in the United States [2]. However, this likely underestimates the true incidence, as there are many mild traumatic brain injuries that go unreported or unrecognized [3]. The term concussion is synonymous with mild traumatic brain injury, however the term concussion may be used to describe instances where the individual experiences transient alteration in mental status, such as from a sports related head injury, whereas a mild TBI is used in the general medical context [4]. A mTBI is defined as an injury with Glasgow Coma Scale of 13–15 with loss of consciousness less than 30 min and post - traumatic amnesia less than 24 hrs. Overall, terms such as concussion, mild head injury, and mild TBI are often used interchangeably to describe the physical injury itself as well as its immediate and later symptomatic consequences [5].

Mild TBI results in a constellation of physical, cognitive, vision, emotional and sleep-related disturbances. Signs and symptoms are broad and include headache, dizziness, gait disturbance, nausea, vomiting, photophobia, trouble focusing, and fatigue. Symptoms may last from several minutes to days, weeks, months or even longer in some cases [6,7]. Headache is the most common physical complain after traumatic brain injury (i.e. TBI) and historically is more common in patients with mTBI, with incidence ranging from 30-90% [8]. Current treatment of those with mTBI has been physical and cognitive rest, as about 80-85% of patients with a concussion will recover to their neurological baseline within 1-2 weeks with this treatment [2]. Similarly, it is believed that most patients with Post Traumatic Headaches (PTH) recover within a few weeks. However, studies have shown 15-42% of patients reporting PTH at 3 months, and 36% at 6 months [8].

Patients who do not recover after three months after a mTBI are categorized as having post concussive syndrome (PCS), which affects approximately 15% of patients [6,7]. A longitudinal study assessing 285 patients with PCS found that 27% of the population studied eventually recovered and 67% of those who recovered did so within the first year [8]. In this study, no patient recovered who had PCS lasting 3 years or longer. Symptoms included persistent headaches and depression. Guidelines for management of PCS have not been completely established, and patients are generally recommended to continue physical and cognitive rest.

Osteopathic Manipulative Therapy (OMT) is a nonpharmacological, noninvasive form of manual medicine. Osteopathic practitioners use a wide variety of therapeutic manual techniques to improve physiological function and help restore homeostasis in the body. There is a structural assessment is to identify possible abnormalities of tissue texture. Areas of asymmetry and misalignment of bony landmarks are also evaluated, along with the quality of motion, balance, and organization. These asymmetries, also known as somatic dysfunctions, are then treated by a variety of manual treatments, administered by osteopaths [10].

There has been research showing the effectiveness of OMT in the treatment of various types of headaches. A recent systematic review assessed 6 studies with various

types of headaches including tension-type headaches, migraine headache, all which showed statistically significant changes in various outcome measures. Outcome measures included the Headache Impact Test (HIT-6) score, headache pain intensity / frequency, and HRQoL [10]. A randomized control trial studied 62 patients with tension-type headaches, and showed that manual therapy techniques to the suboccipital region offered a positive improvement in some aspects of the patient's quality of life [11]. Another systematic review assessing migraine type headaches showed a preliminary low level of evidence that OMT is effective in the management of headache [12]. Overall, studies concluded that more rigorous designs and methodology are needed to strengthen the evidence that OMT has benefit in headache management.

Less has been studied regarding OMT in the treatment of symptoms related to concussion and post traumatic headaches. In our review of the literature, three case reports were found of OMT in the treatment of concussion symptoms. One case assessed a 16 year old female who had a chief complaint of headaches, and had significant improvement of overall symptoms after treatment [13]. Another case report examined a 27 year old man with vestibular symptoms, who had symptomatic improvement after OMT [14]. A third case described OMT to a 50 year old female with mTBI, and showed improvements in HIT-6 scale [15].

In the review of literature, we did not find any studies specifically looking at headaches related to post concussive syndrome. However, as shown above, such headaches can persist for a significant amount of time and adversely affect patient's quality of life. With this study, we seek to study the effect of OMT on this population. The techniques that will be utilized in our study are described below:

- 1. Cervical muscle energy using postisometric relaxation Muscle energy is a form of OMT that engages the patient to voluntarily use targeted muscles on request. After physical assessment of the patient's neck and paraspinals, the physician will place him/her into a precisely controlled position in a direction towards the tight or restricted soft tissue barrier. The physician will then instruct the patient to contract equally against the offered counterforce by the physician. This is an isometric contraction where the distance between the origin and insertion of the muscle remains the same. As the muscle contracts there will be a stretch of internal connective tissues. Golgi tendon organs will sense this change in tension and cause a reflex relaxation of the muscle fibers; similar to a negative feedback loop. This reflex relaxation of the muscle will then allow the physician to passively stretch the patient's previously tightened muscle into an improved range of motion in all planes of motion. This process will require isometric contraction
  - for 3-5 seconds, then relax, and repeat for a total of 3 repetitions. Overall objective is to stretch tightened muscles of the neck and improve range of motion and pain tolerance.
- 2. Myofascial Release of cervical paraspinals Myo (muscle) and fascia (fascial, connective tissue) release involves a similar approach to muscle energy, in that, the objective is to engage restrictive barriers. However, the treatment is more superficial directed toward fascial tissues that encompass and compartmentalize all structures of the body. Fascia is normally a flexible and pliable tissue, but under physical trauma or stress the fascia may become tight and restrictive. Steps of the myofascial release will include the physician palpating the patient's neck to identify

an area of restriction. Restrictive barrier will be identified as muscle tension, tenderness or decreased movement of tissue. Once identified, the physician will then move myofascial tissues toward a restrictive barrier, directly applying a traction along the long axis of the muscle being engaged. He will then add transverse forces (clockwise or counterclockwise) towards the restrictive barriers. The patient will be asked to provide slow deep breaths to enhance a relaxation and release of these tight tissues. The physician will then await a "release". This is a palpatory finding that requires a skilled practitioner to assess. It will consist of a feeling that the previously noted tight tissues release in pressure, or "melt away". This may take several attempts. The goal of this approach is to restore functional balance to all integrative tissues in the musculoskeletal system, improve range of motion, pain tolerance and improve lymphatic flow by removing myofascial restrictions.

3. Sub-occipital Release - Sub-occipital release is a more focused form of myofascial release that engages the sub-occipital muscles. This technique focuses on releasing the fascia surrounding the sub-occipital muscles that attach to the C1- C2 vertebrae of the neck. With the patient laying on their back, the physician will place his/her hands just below the occiput or base of the skull. The physician will then cradle the occiput and apply gentle finger pressure using only the fingertips up into the sub-occipital space. This gentle pressure will be continued until tissue starts to soften and release; approximately 30 seconds to one minute of pressure. As the tissue softens, the head will extend back and rest in the physicians palms. The goal of this technique will be to improve pain, stiffness and headaches. [16]

Potential participants, after signing an informed consent, will be identified based on the following criteria:

- Sustained a concussive injury at least 3 months ago
- The injury did not involve any diagnosed bleeding within the brain
- You did not lose consciousness for longer than 30 minutes
- You have no history of severe migraine headaches prior to the injury
- Were 18 years of age or older at the time of the injury
- Are currently receiving treatment as an outpatient with [name]
- You are not currently receiving IV infusions of medications from a headache specialist at the time of treatment
- You do not have a history of rheumatoid arthritis

The research protocol will be designed in the following way:

- 1. A goal of 15 patients are to be enrolled in the study as well as an equal number of 15 control subjects who will not participate in osteopathic treatments. The selected patients will be seen for a total of three visits of which the first two sessions will be treatment visits. All visits will be in 4 week intervals.
- 2. Patients selected to participate in the study will undergo a musculoskeletal examination of the cervical spine. Testing will be comprised of:

- a. Range of motion testing involving cervical rotation, lateral side bending, flexion and extension.
- b. Muscular palpation of the cervical paraspinals for hypertonicity of the muscles and/or tenderness.
- 3. The patient will then be placed supine on the examination table after which treatment will commence.
- 4. Treatment sessions will last for 5-10 minutes each and will be performed by one osteopathic physician. In the time allotted, three OMT techniques will be performed: cervical muscle energy, myofascial release of the cervical paraspinals and a suboccipital release. The three physicians will have met prior to treatment to standardize protocol.
- 5. Patients will be asked to complete the Headache Impact Test (HIT-6) at visit 1 and 2 between about 6 weeks. All patients will also quantify their pain using a pain scale before and after treatment.
  - 6. Change scores between pain scales between treatments will be assessed, and improvements between HIT-6 scores will be analyzed for statistical significance.

### **Recruitment and Informed Consent**

Participants will be recruited from individuals who are being evaluated by [name] for Post Concussive Symptoms.

Written informed consent will be obtained from all enrolled participants accordance with Institutional Review Board (IRB) policies. Potential participants will be informed that there is no penalty for refusal to participate. A quiet private space will be available for the consent process and there will be no time limits. [name], the attending physician, as well as the residents participating in the study will be available to answer any questions or concerns that may arise.

Consent will be in a language that is easily understood by most individuals with at least a 6th grade education and each participant/proxy/informant will have a checklist to follow to ensure they understand study procedures. All participants will be informed that the purpose of the study is to help the participants pain and headaches, and will be informed regarding the resident education component of the study. Time and effort commitments required for study participation will be explained. Verbal feedback will be solicited from potential participants about their understanding of the study, its risks, and potential benefits prior to completion of the written informed consent form. Each potential study participant will be asked to state in his/her own words what the purpose of the study is, what he/she is expected to do, and what the risks and benefits are.

All potential participants (or designated family member/legal guardian) will be given a copy of the written consent form. Prior to signing the consent documents, all potential participants will be given the opportunity to review the consent document, discuss it with whomever they choose (including the study investigators), and take as much time as they need to consider the information that has been presented to them in order to make an informed decision

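### All participants, controls included, are told that the study's purpose is to help their headaches; this non-neutral wording can add, by an unknown amount, to expectation bias already present in an unblinded design with patient-rated outcomes

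*Combined protocol and SAP*

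**What the plan says.** The protocol section on recruitment and informed consent instructs: "All participants will be informed that the purpose of the study is to help the participants pain and headaches". It adds a restating step: "Each potential study participant will be asked to state in his/her own words what the purpose of the study is". The same sentence also asks for the person's account of what is expected of them and of the risks and benefits.

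The protocol's introduction gives a different purpose: "With this study, we seek to study the effect of OMT on this population". Its literature review found three case reports of OMT for concussion symptoms and no study specifically of headache in post-concussive syndrome.

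In the numbered design list, item 1 plans 15 treated patients and "15 control subjects who will not participate in osteopathic treatments". Item 5 names the measures: "Patients will be asked to complete the Headache Impact Test (HIT-6) at visit 1 and 2", and "All patients will also quantify their pain using a pain scale before and after treatment". Item 6 names what is analysed: "Change scores between pain scales between treatments will be assessed, and improvements between HIT-6 scores will be analyzed for statistical significance".

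The Statistical Plan tests VAS change from before to after treatment with a signed-rank test in the treated group alone. It compares HIT-6 change between groups with a rank-sum test. Neither document describes a sham procedure, blinding or a masked assessor.

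**The concern.** Whether OMT helps is the question under study. A participant who is told that the study exists to help their headaches hears an aim of benefit where the research aim is neutral, and is asked to say it back before consenting. For a control the statement fits poorly, because no OMT is given and no other study intervention is described.

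The statistical stake is reporting bias. Patients will know whether they had hands-on treatment, and they score both outcomes themselves. Any expectation raised by the wording has no objective or masked endpoint to check it. In groups of 10 to 15, even a modest shift in ratings moves the chance of a significant result well away from 5%.

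**Working it through.** **1. The texts side by side.** The introduction sets out to study an effect; the consent section announces help. The first leaves benefit open, as the cited evidence requires. The second does not say that benefit is unknown. It is addressed to everyone, including the controls of item 1.

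**2. How expectation enters each test.** Let δ be the true effect, and let b_T and b_C be the expectation shifts in treated and control patients.

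- VAS, treated group only: expected mean change = δ + b_T. There is no comparator, so b_T enters in full.
- HIT-6, between groups: expected difference = δ + (b_T − b_C). A shift common to both groups cancels. Only a differential shift, arising once patients know their group, biases the result.

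**3. The plan's own figures, to confirm the inputs.** The Statistical Plan assumes a two-sided 5% level, SD 2 for VAS change (n = 10, change 2) and SD 8 for HIT-6 (10 per group, difference 10).

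- VAS: Φ(√10 × 2/2 − 1.96) = Φ(1.202) = 0.885, against 89% stated.
- HIT-6: Φ(10 / (8 × √(2/10)) − 1.96) = Φ(0.835) = 0.798, against 80% stated.

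Both agree with a normal approximation. Simulating the planned Wilcoxon tests with normal data gives about 0.78 and 0.70. This point does not depend on either power figure.

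**4. Sensitivity to a total bias of assumed size.** The documents give no size for any expectation shift, so the shifts below are assumptions. The true effect is zero, the data are normal with the plan's SDs, the p-values are exact, and each entry uses 200,000 simulations.

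| Test | Assumed total bias | Significant, n = 10 (per group) | Significant, n = 15 (per group) |
|---|---|---|---|
| VAS signed-rank | 0 | 5% | 5% |
| | 0.5 | 10% | 14% |
| | 1.0 | 28% | 42% |
| | 1.5 | 54% | 75% |
| HIT-6 rank-sum | 0 | 4% | 5% |
| | 2 (differential) | 7% | 9% |
| | 5 (differential) | 23% | 35% |

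The 10s are the Statistical Plan's numbers and the 15s are the protocol's enrolment goal. The table is the planned tests' rejection rate for bias from any source.

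**5. What a change of wording might buy.** Suppose, purely for illustration, that the total VAS bias is 1.0 point and the sentence supplies 0.25 of it. Neutral wording leaves 1.0 − 0.25 = 0.75, and the n = 10 rejection rate falls from about 28% to about 18%, not to 5%. If the sentence supplies nothing, the rate stays at 28%.

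**The case against.** The strongest reply is that the bias comes from the design. Patients offered manual treatment for headache by the clinic that treats them will infer its aim under any wording, and the untreated controls and uncontrolled VAS test do the rest. That stands: the sentence can add to the bias but does not create it. A reader might take the 10% to 54% and 7% to 35% figures as false-positive rates caused by the sentence. The documents do not support this, because nothing in them separates the wording's share from the total.

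A reader might also infer that any expectation shift adds straight to both results. That holds for VAS only. Everyone hears the same sentence, so a common shift cancels in HIT-6, and the size and direction of any shift in controls are not known.

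Two further readings go past the text. An aim to help is not an assertion that benefit is established, and the protocol elsewhere says only that improvement is hoped for and lists possible worsening of headache and neck pain. Nor does the sentence mention OMT or groups, so the idea that it tells controls they are missing the useful part is inference.

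Finally, the consent form is not among the documents and may already be neutral, and the checklist is described as covering study procedures, with no item on purpose shown. Participants must also restate risks and benefits. These points limit the claim. They do not correct a purpose that the protocol tells staff to give and that disagrees with its own aim.

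**Conclusion.** The point holds as a wording defect with a plausible but unquantified statistical consequence. Three things are certain from the text: the instruction applies to all participants, it differs from the protocol's neutral aim, and it does not fit controls. That the trial is open is inferred from the untreated control group and the absence of any sham or blinding, since the documents do not use the term.

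Given that, the wording can enlarge expectation bias in VAS directly, and in HIT-6 only through a difference between groups. Its separate size is unknown and could be zero. The simulated rates rest on assumed total shifts, the plan's SDs and normal data, and should be labelled as sensitivity to total bias wherever they are used. The change is worth making because it is cheap and the text is clear, not because a given false-positive rate has been traced to it.

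**What to change.** Replace the sentence with neutral wording used identically in both groups, for example: 'All participants will be informed that the purpose of the study is to find out whether OMT changes headache and pain after concussion, and that it is not known whether it does.' Check the consent form, and any checklist item on purpose, and align them if they differ.

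The Statistical Plan is written in the past tense. If consent is already complete, report the wording as a limitation when interpreting VAS and HIT-6.

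The cost is a minor wording amendment through the IRB, with no new procedures, staff or sample size. It reduces expectation bias by an unknown amount and leaves the part due to lack of blinding and to the uncontrolled VAS comparison.

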### **Potential Risks**

There are no anticipated physical or medical risks associated with participation in the study. There will be no high velocity or high impact techniques that would cause any harm. There may involve some temporary discomfort during the procedure and worsening of headache and neck pain. There is very little risk of any foreseeable psychological, social, legal, or financial risks or harms that might result from participating in this research study. There is very little risk of any orthopedic or musculoskeletal injuries that would result from the treatment.

## **Protection Against Risks**

All treatment will be conducted by osteopathic physicians (Doctors of Osteopathy i.e. DO), and residents will be supervised under the attending physician [name], DO.

Participants will be informed at the time of consent that they will be offered treatment by JFK Medical Center in the event of a medical emergency, although the costs of this treatment will not be included as part of the research. Participants will be informed that they can withdraw their consent to participate at any time during the study without any consequences to them and their access to medical services.

Confidential information will be protected by separating identifying material from data files and securing files in locked cabinets and/or password protected encrypted electronic files. JFK-JRI has internal security measures to further protect digital data, including identifying medical and clinical data, as per HIPAA requirements. Participants (or proxies) will be informed that identifying records may be inspected by the sponsoring agency or by the IRB and, therefore, absolute confidentiality cannot be assured.

# Importance of the Knowledge to be Gained

We anticipate that the information gathered will make a significant contribution to the knowledge and understanding of the treatment of headaches with OMT. We hope that the treatment will improve symptomatology. We hope to provide an educational component to the other Physical Medicine and Rehabilitation residents in the program as well to increase the awareness and use of OMT in clinical practice.

# Statistical Plan (last update on July 15, 2017)

JMP version 14.1 (SAS Institute Inc) was used for statistical analysis. Descriptive statistics (mean, median, SD) and graphical (box plots, bar charts) methods were used. For the treatment group, a paired Wilcoxon signed rank test was performed to assess the change in VAS data from pretreatment to posttreatment. With 10 patients, we had 89% power to detect a change of 2 in the VAS scores from pretreatment to posttreatment, assuming a 2-sided significance level of 5% and a standard deviation of 2 (effect size =1). The Wilcoxon rank sum test for continuous (eg, age) and discrete (eg. variables (eg, change in HIT-6 scores, time from injury to visit [months]) and the Pearson x2 test for categorical variables (eg, mechanism of injury, history of prior MTBI) were performed for comparison of the treatment and control groups. With 20 patients (10 per group), we had 80% power to detect a difference in the means of 10 between the groups in HIT-6, assuming a standard deviation of 8, and a 2-sided significance level of 5%. Two-sided P value <.05 was considered statistically significant.

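### The only VAS test stated is an uncontrolled before/after test in the treated group, so it cannot show an OMT effect, and neither stated power is reached by the planned rank test

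*Combined protocol and SAP*

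**What the plan says.** The Statistical Plan gives one test for VAS: "For the treatment group, a paired Wilcoxon signed rank test was performed to assess the change in VAS data from pretreatment to posttreatment". It has its own power statement: "With 10 patients, we had 89% power to detect a change of 2 in the VAS scores from pretreatment to posttreatment", with two-sided 5% significance and SD 2.

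The treated and control groups are compared by Wilcoxon rank sum test for a list of example variables that includes "change in HIT-6 scores, time from injury to visit [months". VAS is not in that list. The only between-group power statement concerns HIT-6: "we had 80% power to detect a difference in the means of 10 between the groups in HIT-6", with SD 8 and 10 per group. One rule covers every test: "Two-sided P value <.05 was considered statistically significant". No primary outcome is named.

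The protocol's design list (item 1) plans 15 treated patients and "15 control subjects who will not participate in osteopathic treatments". It describes neither random allocation nor a sham procedure. Item 4 states "Treatment sessions will last for 5-10 minutes each", and item 5 has pain rated before and after treatment. Item 6 says that pain change scores will be assessed, and mentions statistical significance only for HIT-6.

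**The concern.** The VAS test asks whether treated patients' scores move. It does not ask whether they move more than they would without OMT. On the most natural reading of items 4 and 5, the two ratings bracket a short session. Lying at rest, expectation, ordinary fluctuation and regression to the mean would then all count towards significance. Expectation is a real possibility here, because Recruitment and Informed Consent says participants are told that the study aims to help their pain and headaches. If the ratings span visits instead, natural recovery counts as well.

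Followed as written, the plan could yield a significant pain result beside a null HIT-6 comparison, both judged by the same rule. The pain result would not be evidence for OMT. The stated 89% is power against no change, so it says nothing about the chance of showing a benefit over control. It is also higher than the planned test delivers.

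**Working it through.** **Inputs from the Statistical Plan.** VAS: n=10, change 2, SD 2, two-sided 5%. HIT-6: 10 per group, difference 10, SD 8 (read as the per-arm SD of the analysed value), two-sided 5%.

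**Reproducing the stated powers.** Both follow from a normal approximation.
- VAS: Φ((2/2)·√10 − 1.960) = Φ(3.162 − 1.960) = Φ(1.202) = 0.885, against 89% stated.
- HIT-6: Φ(10/(8·√(2/10)) − 1.960) = Φ(2.795 − 1.960) = Φ(0.835) = 0.798, against 80% stated.

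**Power of the planned tests.** t-test values come from the noncentral t distribution. Rank-test values come from simulation with continuous normal data.

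| Test | Stated | Normal approx. | t-test | Planned rank test |
|---|---|---|---|---|
| VAS, n=10 | 89% | 88.5% | 80% | about 79% (exact signed rank, reject if W≤8) |
| HIT-6, 10 per group | 80% | 79.8% | 75% | about 71% (exact rank sum, reject if U≤23); about 74% (normal-approximation P value without continuity correction, U≤24) |

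The exact signed rank test first reaches 89% at n=13. If pain is scored in whole numbers, which the documents do not state, ties and zero changes lower the VAS power further. Rounding the changes to whole numbers, dropping zeros and using an exact tied P value gives about 73%.

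**What the VAS test responds to.** The documents give no value for non-specific change, so a range is assumed. OMT effect is zero, SD of change is 2, and the test is the exact signed rank.

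| Assumed non-specific change (VAS points) | Significant, n=10 | Significant, n=15 |
|---|---|---|
| 0 | 4.9% | 4.8% |
| 0.5 | 11% | 14% |
| 1.0 | 28% | 42% |
| 1.5 | 54% | 75% |
| 2.0 | 78% | 94% |

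The first row shows that the test holds its level when nothing changes. The last row is the test's own power at the plan's target change: the test cannot tell where a 2-point change came from.

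**A comparison with controls, if the data exist.** For a 2-point difference with an assumed SD of change of 2 in each arm, exact rank sum power is about 51% at 10 per group and about 72% at 15.

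**The case against.** The case on the other side is substantial, and much of it stands.

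- **The test is openly one-arm.** The sentence begins by restricting it to the treatment group. A reader might infer that the plan presents a significant VAS change as proof of OMT efficacy, but neither document says so. The risk lies in the inference that the plan leaves open.
- **A between-group VAS test is not ruled out.** The list of compared variables is introduced as examples. A reader might infer that such a test is excluded. The text supports only that none is named or powered.
- **HIT-6 has some textual priority.** Protocol item 6 attaches statistical significance to HIT-6 alone, so it would be too strong to say that nothing favours HIT-6. It does not settle the ranking, because the Statistical Plan tests both outcomes at the same threshold.
- **It is partly a design limit.** Untreated controls have no session, so they may have no matching before/after ratings, and the within-group test may be the only one available.
- **HIT-6 is no clean alternative.** With no randomisation or sham described, that comparison keeps expectation effects and is open to selection effects.
- **The illustration is assumed.** No non-specific change is given, and Potential Risks allows that headache and neck pain may worsen, so it could run the other way. Nor is it type I error inflation, although the percentages could be misread that way.

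None of this makes the VAS test able to attribute a change to OMT, and none of it restores the stated powers.

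**Conclusion.** The point holds in a limited form. The only stated VAS test is uncontrolled, and a significant result from it is evidence of change in treated patients, not of an OMT effect. It does not reach the whole trial, because change in HIT-6 is compared between groups. How often a misleading VAS result would arise cannot be fixed from the documents; the 11% to 78% range at n=10 depends on the assumed change of 0.5 to 2 points.

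The power finding needs no outside figure. On the plan's own inputs and continuous normal data, the planned tests give about 79% for VAS and about 71% to 74% for HIT-6, about 10 and 6 to 9 percentage points below the stated values. This applies to the 10 per group used in the Statistical Plan. With the protocol's 15 per group analysed, the exact tests would give about 94% and 89%.

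**What to change.** 1. **VAS.** Report the treated-group change as descriptive, with an estimate and 95% CI. State that it is uncontrolled, and draw no OMT efficacy conclusion from it.
2. **Efficacy.** Rest any efficacy statement on the between-group change in HIT-6, and note that no randomisation or sham is described. The Statistical Plan is written in the past tense. If this ranking is set after data were seen, say so and do not call it prespecified.
3. **Power.** Restate both figures for the planned tests, with assumptions: VAS about 79% at n=10 against no change (lower with whole-number scoring and ties), and HIT-6 about 71% to 74% at 10 per group, depending on how the P value is computed.
4. **Controls.** Only if controls already have matched pain ratings, add the between-group difference in VAS change as supportive, with its power (about 51% at 10 per group, 72% at 15, SD of change 2 assumed) and the caveat in item 2.

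Items 1 to 3 need wording only, and item 4 needs no new data if the ratings exist. The price is a weaker VAS claim and two less favourable powers. For example, a mean change of 2 with SD 2 at n=10 would be reported as 2.0 (95% CI about 0.6 to 3.4, half-width 2.262·2/√10 = 1.43), with no statement about OMT.

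Visit timing is a separate point: "All visits will be in 4 week intervals" in protocol item 1 conflicts with the roughly 6 weeks between visits 1 and 2 in item 5, and the two should be reconciled.
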